9.1.1. Incidence of Adverse Events

An overall summary of TEAEs will be presented by treatment group and will include the number and percentage of patients with at least one TEAE, any serious TEAEs, any fatal TEAEs, and any TEAEs leading to discontinuation of study drug. The 95% confidence intervals for these percentages by the Clopper-Pearson method will be presented. Similarly, the number of patients experiencing these events will be compared at each level of active S-600918 dosing to placebo using Fisher's exact test.

The number and percentage of patients with TEAEs will be summarized by SOC and PT for each treatment. All AEs will be presented in a listing.

9.1.2. Relationship of Adverse Events to Study Drug

An overall summary of treatment-related TEAEs will be presented by treatment group and will include the number and percentage of patients with at least one treatment-related TEAE, any serious treatment-related TEAEs, any fatal treatment-related TEAEs, and any treatment-related TEAEs leading to discontinuation of study drug. The 95% confidence intervals for these percentages by the Clopper-Pearson method will be presented.

The number and percentage of patients with treatment-related TEAEs will be summarized by SOC and PT for each treatment.

9.1.3. Severity of Adverse Event

The number and percentage of patients with TEAEs by severity will be presented by MedDRA system organ class and preferred term for each treatment group. Each patient will be counted only once within a preferred term or system organ class at the most extreme observed level of severity.

9.1.4. Serious Adverse Events

The number and percentage of patients with serious TEAEs at any time will be summarized by SOC and PT for each treatment. All serious TEAEs will be presented in a separate listing.

9.1.5. Adverse Events Leading to Treatment Discontinuation

The number and percentage of patients with TEAEs leading to discontinuation of study drug will be summarized by SOC and PT for each treatment. All TEAEs leading to discontinuation of study drug will be presented in a separate listing.

9.1.6. Death

All TEAEs with an outcome of death will be presented in a separate listing.

9.1.7. Subgroup Analyses for Adverse Events

The number and percentage of patients with TEAEs will be similarly summarized for each treatment by Region (United States, Europe, Japan).

Forest plots of the relative risk and its 95% confidence interval of TEAEs between each active treatment group and placebo will be presented for the subgroups above for TEAEs.

9.1.8. Taste Changes

The number and percentage of patients with any treatment-emergent adverse events that reflect taste change as defined using the Standardized MedDRA Query (SMQ) category of "Taste and smell disorders" will be summarized by SOC and PT for each treatment group.

As well, the number and percentage of patients with any treatment-emergent adverse events shown in Table 9-1 will be summarized by SOC and PT for each treatment group.

Preferred	System Organ	Preferred Terms Name	System Organ Class Name
Terms Code	Class Code		, ,
10001480	10029205	Ageusia	Nervous system disorders
10013911	10029205	Dysgeusia	Nervous system disorders
10019071	10037175	Hallucination, gustatory	Psychiatric disorders
10020989	10029205	Hypogeusia	Nervous system disorders
10064480	10022891	Gustometry abnormal	Investigations
10069147	10029205	Hypergeusia	Nervous system disorders
10082490	10029205	Taste disorder	Nervous system disorders

Table 9-1: Adverse Events Reflecting Taste Change

Responses to the taste questionnaire will be summarized descriptively and listed.

9.2. Clinical Laboratory Evaluations

Clinical laboratory samples will be analyzed using a central laboratory, and results will be provided in SI and US units with the appropriate normal ranges. All laboratory results will be listed.

The results from the samples collected at Visit 2, Visit 4, Visit 6, and Visit 7 will be summarized using at each visit. For continuous results, both the results and change from baseline of the results will be summarized. Continuous chemistry, hematology, and urinalysis results will be summarized using SI units and US units.

Chemistry results except for blood urea nitrogen and total protein and hematology results except for hematocrit, erythrocytes (red blood cells), basophil count, and monocyte count will be categorized according to CTCAE version 5 and listed. Cross tables of these grades at Visit 2 and each of Visit 4, Visit 6 and Visit 7 will be prepared by each parameter. For the cross tables, grades will be summarized using SI units for patients enrolled at sites outside the United States and using US units for patients enrolled at sites.

Qualitative results for urinalysis will be summarized by the number and percentage of patients with results in each category by treatment group at each visit.

Significant abnormalities will be defined for ALT, AST, and Total Bilirubin. An AST or ALT result >3 x ULN and a total bilirubin value >2 x ULN will be considered an abnormality. The number and percentage of patients experiencing either and both of these abnormalities after the first dose of study drug up through the follow-up visit will be summarized by treatment group. As well, the number and percentage of patients experiencing an AST results >3 x ULN, an ALT results >3 x ULN, an AST or ALT results >5 x

ULN, prothrombin time international normalized ratio (PT-INR) >1.5, and (an AST or ALT result >3 x ULN) and (a total bilirubin value >2 x ULN or PT-INR >1.5) will be summarized. A separate listing will present all ALT, AST, and total bilirubin results for any patients with either abnormality.

Numbers of patients and their proportions whose creatinine increased more than 0.3 mg/dL for patients enrolled in the United States or more than 26 umol/L for patients enrolled outside of the United States from Visit 2 at each of Visits 4, 6, 7 and any time point during treatment period and follow-up period will be summarized. A separate listing will present all creatinine results for any patients with an increase greater than 0.3 mg/dL from Visit 2.

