3.4. Dose Adjustment/Modifications

No dose adjustments or modifications are allowed in this study.

4. General Statistical Considerations

Unless otherwise noted, continuous variables will be summarized based on the number of non-missing observations (N), arithmetic mean (Mean), standard deviation (SD), median, minimum, and maximum values. Categorical variables will be summarized based on the frequency count and the percentage of patients in each category. All statistical tests will be performed at the 0.05 significance level using 2-sided tests, unless otherwise noted, and statistical testing will not be adjusted for multiple comparisons.

Study data will be presented in by-patient data listings. In general, all tables will be presented by treatment group. Individual patient data, PK data, and any derived data will be presented by treatment group (study drug) (S-600918 50 mg, S-600918 150 mg, S-600918 300 mg, and placebo). All analyses and tabulations will be performed by using SAS Version 9.2 or higher and WinNonlin Version 6.3 or higher.

Baseline will be defined as the last valid assessment recorded prior to the first administration of study drug unless otherwise specified.

For summaries, patients will be counted only once within each planned visit. In these summaries, the visit windows will follow the windows given in the protocol, which are repeated in Appendix 1 of this SAP. However, +1 day will be allowed at the end of the Visit 6 time window for analysis.

Visit	Target Day	Window Start Day	Window End Day
Visit 1 / Screening	-18	-28	-18
Visit 2 / Day -1	-1	-1	-1
Visit 3 / Day 1	1	1	1
Visit 4 / Day 8	8	6	10
Visit 5 / Week 3	22	20	24
Visit 6 / Week 4	27	25	28

Table 4-1: General Analysis Visit Wind

In the event that more than one observation is recorded within one of these windows, then, among these records within the window, the record occurring at the planned visit in the CRF will be used. If no records occurred at the planned visit within the window, then records occurring at any unplanned visits within the visit window will be considered, and the record occurring closest in time to the target visit day will be used. Results that are recorded at an Early Discontinuation visit may be summarized at a planned visit if the Early Discontinuation visit falls within the window for the planned visit, and the planned visit has not occurred.

Study days will be calculated using the date of the first administration of study drug as follows:

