- If the assessment occurs on or after the date of the first administration of study drug, study day = (date of assessment – date of first administration of study drug) + 1
- If the assessment occurs prior to the date of the first administration of study drug, study day = date of assessment – date of first administration of study drug

Summaries presented by visit will only present the visits for which the parameter was planned to be collected. Listings of data collected at study visits will include all such data, regardless of whether it was planned to be collected during that visit.

Certain regional guidelines provide that patient reported outcomes (PROs) can be re-entered, or corrected, by the patient after the initial entry. This study uses several PROs, such as VAS, LCQ, ICIQ-SF, SF-36, PGIC, and Taste Questionnaire. As such when the original data are corrected, analyses will be conducted that use the latest available corrected data. For patients who did not correct their original entry, their original entry will be used in these analyses of corrected data. Additional analyses of only the original data will also be performed.

The following conventions define how the original data and corrected data will be analyzed. If there are no data corrections, then these conventions do not apply.

Analyses on the full analysis Set will use the latest corrected data, regardless of when the correction was obtained. A footnote to all tables containing corrected data will note how many instances of corrected data were included. These analyses will be included in the body of the CSR and will be the basis of hypothesis testing.

These analyses will be repeated using the original entries. Any differences in inference between the analysis of the corrected data and analysis of the original data will be noted in the CSR.

There is no plan for analyzing the PRO data using a Per Protocol Set. However, if this plan changes during or after the study, the Per Protocol Set will use corrected data only if the corrected data falls within the protocol defined window for a visit. Corrected data collected outside a visit window will not be

included in the Per Protocol Set population. A supplemental Per Protocol Set analysis will be conducted using only the original collected data. Any difference in the conclusions based on the Per Protocol Set between the use of the original and corrected data will be noted in the CSR if the CSR has not yet been completed.

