9.3. Vital Sign Measurements

Blood pressure and pulse rate will be recorded at each visit in the study. Observations at Visit 3, Visit 4, Visit 5, Visit 6, and Visit 7 will be summarized using descriptive statistics. The change from baseline will also be summarized for these Visit 4, Visit 5, Visit 6, and Visit 7, with baseline defined as the last observation prior to the first administration of study drug. All vital signs data will be listed.

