9.5. Electrocardiogram

Qualitative assessments of electrocardiograms (ECG) conducted at Visit 1, Visit 2, Visit 6, and Visit 7 will be summarized by treatment group and by visit according to the number and percentage of patients reporting an ECG result in each result category. These assessments will be reported as normal, abnormal-not clinically significant, or abnormal-clinically significant.

10. Pharmacokinetics

All presentations of data related to pharmacokinetics will be presented for the PK Concentration Population.

Individual plasma concentrations of S-600918 and its metabolite S-600918 acyl glucuronide will be listed with the actual time elapsed from administration of the last dose by patient and plotted against the actual time elapsed from the last dose. In addition, plasma concentrations of S-600918 and S-600918 acyl glucuronide within 20 to 28 hours after the last dose will be summarized as plasma trough concentrations (C_{trough}) by dose and scheduled visit (Visit 4 and Visit 6) with N, Mean, SD, and coefficient of variation (CV%, calculated by SD/Mean × 100); geometric mean (Geometric Mean) and coefficient of variation for geometric mean (CV% Geometric Mean); and median, minimum (Min) and maximum (Max) values. The CV% Geometric Mean will be calculated according to the following formula: CV% Geometric Mean = [exp (sd²) - 1]^{1/2} × 100, where sd is the standard deviation for natural log (In) - transformed data.

The relationships between C_{trough} and dose will be presented graphically by scheduled visit (Visit 4 and Visit 6) for S-600918 and for S-600918 acyl glucuronide. If C_{trough} is below the lower limit of quantitation, Mean, SD, CV%, Min, Median, and Max will be calculated as 0, and that value will not be included in the calculation of Geometric Mean and CV% Geometric Mean.

Plasma drug and metabolite concentrations determined in blood samples obtained outside of allowable time windows will be included in PK analyses and will not be handled as missing data. Individual plasma concentrations, if deemed to be anomalous, may be excluded from the analysis at the discretion of the PK analyst. Any such exclusion will be communicated to the sponsor and clearly represented in the study report along with justification for exclusion.

Descriptive statistics for Ctrough will be presented as follows:

- N: no decimal place
- Mean, Geometric Mean, SD, median, Min, and Max: same precision as per the observed values.

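### The CTCAE shift tables and ECG summaries depend on planned-visit windows and have no worst post-baseline or end-of-treatment row, so most Early Discontinuation laboratory and ECG results could miss them

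*SAP*

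**What the plan says.** The safety summaries are organised by planned visit.

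- **Laboratory (SAP 9.2).** "The results from the samples collected at Visit 2, Visit 4, Visit 6, and Visit 7 will be summarized". The CTCAE grades are then cross-tabulated: "Cross tables of these grades at Visit 2 and each of Visit 4, Visit 6 and Visit 7 will be prepared by each parameter".
- **Vital signs (SAP 9.3).** "Observations at Visit 3, Visit 4, Visit 5, Visit 6, and Visit 7 will be summarized using descriptive statistics".
- **ECG (SAP 9.5).** "Qualitative assessments of electrocardiograms (ECG) conducted at Visit 1, Visit 2, Visit 6, and Visit 7 will be summarized by treatment group and by visit".

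SAP Section 4 (General Statistical Considerations) sets three rules for results obtained elsewhere.

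- **By-visit rule.** "Summaries presented by visit will only present the visits for which the parameter was planned to be collected".
- **ED rule.** "Results that are recorded at an Early Discontinuation visit may be summarized at a planned visit if the Early Discontinuation visit falls within the window", on the further condition that the planned visit has not taken place.
- **Unplanned-record rule.** If no planned-visit record lies in the window, "records occurring at any unplanned visits within the visit window will be considered", and the one nearest the target day is used.

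The protocol calls for laboratory tests, blood pressure and pulse, and ECG at the ED Visit (Sections 7.6.2.1, 7.6.3, 7.6.4 and 8.8). After a qualifying liver abnormality it asks for repeat liver tests two to three times a week (Appendix 2).

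SAP 9.2 also has summaries that are not tied to a visit. It counts AST/ALT above 3 x ULN and bilirubin above 2 x ULN from first dose through follow-up. It adds further AST/ALT and PT-INR threshold counts with no visit restriction, and a creatinine-rise count that includes any time point. No worst post-baseline grade, ECG category or vital-sign value is planned.

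**The concern.** An ED Visit often supplies the last laboratory set and ECG obtained on or close to treatment. The protocol collects these results, but the SAP gives many of them no place in the laboratory and ECG tables that compare arms. For a patient who stops between Visit 4 and Visit 6, the CTCAE cross tables can hold a Visit 4 grade and a Visit 7 grade with nothing between. For a patient whose ED Visit falls before Day 25, the only post-dose ECG summarised would normally be Visit 7, two weeks after the last dose.

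This is a dose-selection study without an independent data monitoring committee, so the by-arm safety tables carry weight. If discontinuation differs by dose, so does the share of on-treatment results missing from those tables.

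**Working it through.** The plan states no figure on this point, so there is none to reproduce. The check counts the days on which an ED result could enter a table.

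**Inputs.** The analysis windows in SAP Table 4-1 are Visit 4 Days 6-10 (5 days), Visit 5 Days 20-24 (5 days) and Visit 6 Days 25-28 (4 days). Visit 7 has no row. According to the schedule in Appendix 1, the on-treatment visits after first dose are Visits 4 and 6 for laboratory tests, Visit 6 for ECG, and Visits 4, 5 and 6 for blood pressure and pulse.

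**Assumption (not in the documents).** ED visits are spread evenly over Days 2-28, which is 27 days.

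**Formula.** Share left out = (27 - admissible days) / 27. The first result column assumes no planned record has taken precedence. The second assumes each planned visit was held on its target day (8, 22, 27), so that only ED days before the target are admitted.

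| Result | Days in window | Left out, no planned record yet | Left out, planned visit on target day |
|---|---|---|---|
| Laboratory, CTCAE grade | 5 + 4 = 9 | 18/27 = 67% | (27 - 4)/27 = 85% |
| ECG | 4 | 23/27 = 85% | (27 - 2)/27 = 93% |
| Blood pressure, pulse | 5 + 5 + 4 = 14 | 13/27 = 48% | (27 - 6)/27 = 78% |

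The last column does not count the target day as admitted, because a patient who stops at a scheduled visit has no separate ED Visit. Counting it as admitted gives 21/27 = 78%, 24/27 = 89% and 18/27 = 67%.

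**Sensitivity to the range of days (first result column).** Over Days 2-27 the shares are 18/26 = 69%, 23/26 = 88% and 13/26 = 50%. Over Days 2-31, which allows for the +3-day ED window, they are 21/30 = 70%, 26/30 = 87% and 16/30 = 53%.

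**Stopping on a scheduled visit day.** Protocol 8.8 has the ED assessments done at that visit. At Visit 5 this produces laboratory tests and an ECG, and at Visit 4 an ECG. None of these is planned at the visit concerned, so the by-visit rule keeps them out of its tables.

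**Repeat liver tests.** If a planned record exists in the window, it is used and the repeat is not. If none exists, the repeat nearest the target day is used, which need not be the worst. Repeats still feed the threshold counts and the listings.

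**The case against.** The strongest reply is that significant toxicity reaches the arm comparison by other routes.

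- **Adverse events.** Protocol 7.6.5.6 requires a test result to be treated as clinically significant, and so recorded as an adverse event, if it leads to a dosing change, discontinuation from the study, therapy or further diagnostic work. Those events enter the by-arm TEAE tables (SAP 9.1.1, with Fisher's exact test for the overall categories), the severity tables (9.1.3) and the tables of events leading to discontinuation (9.1.5). This stands, and it narrows the harm considerably.
- **Liver and creatinine.** A reader might infer that all extra liver-monitoring results are lost. They are not. Every Appendix 2 criterion that triggers monitoring requires AST or ALT above at least 3 x ULN, so the patient is already in the SAP 9.2 counts. What those counts do not show is peak grade: the highest AST/ALT count is at 5 x ULN, while Appendix 2 also uses a threshold of 8 x ULN.
- **Planned visits only.** A reader might infer this too. In-window ED and unplanned results are admitted under SAP Section 4.
- **Listings.** All laboratory and vital-sign data are listed, and listings include results from unplanned visits. No data disappear, but a listing does not compare arms.
- **Consistency with the protocol.** Protocol 9.12.2 to 9.12.4 specify summaries by observation point, so the SAP contradicts nothing. The issue is an omission.
- **Size.** Even timing of ED visits has no support in the documents. The 10% in the sample-size section is an allowance for exclusions, not a discontinuation rate, so no number of affected patients can be derived from it.

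**Conclusion.** The point holds in a limited form. ED laboratory results outside Days 6-10 and 25-28, and ED ECGs outside Days 25-28, enter no CTCAE cross table or by-visit summary, and no worst post-baseline table makes up for this. With even timing over Days 2-28, that is 67% of ED laboratory sets and 85% of ED ECGs, rising to 85% and 93% if planned visits were held on target and take precedence. For blood pressure and pulse it is about half (48%) on the basic count, so it is not established that most are left out.

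The gap covers graded laboratory parameters other than those with threshold counts, peak CTCAE grade for all of them, ECG category and vital signs. It does not cover AST/ALT, bilirubin, PT-INR or creatinine threshold crossings, or abnormalities recorded as adverse events.

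A reader might go further and infer that the plan understates toxicity, because the omitted results come from the patients with the most of it. That is plausible but not shown. Protocol 4.5.2 also lists patient request and other reasons for stopping, and the documents give no data on timing or reasons by arm.

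**What to change.** Keep the by-visit tables as they are, and make two additions.

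1. Add to SAP 9.2 (CTCAE grade) and 9.5 (ECG category), and to 9.3 for blood pressure and pulse, a baseline-to-worst post-baseline table by arm. It should cover first dose to Visit 7 and use all scheduled, unscheduled and ED results.
2. Add an end-of-treatment row to the same sections, holding the Visit 6 result or, for early discontinuers, the ED result.

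It would also help to state a Visit 7 window, which Table 4-1 lacks.

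The cost is SAP wording and a few extra tables, with no new data. One caution is that a worst value depends partly on how often a patient was tested, which is a reason to read the new tables beside the by-visit ones.

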9.3. Vital Sign Measurements

Blood pressure and pulse rate will be recorded at each visit in the study. Observations at Visit 3, Visit 4, Visit 5, Visit 6, and Visit 7 will be summarized using descriptive statistics. The change from baseline will also be summarized for these Visit 4, Visit 5, Visit 6, and Visit 7, with baseline defined as the last observation prior to the first administration of study drug. All vital signs data will be listed.

9.4. Physical Examination

A physical examination will be performed at each visit, except for Visit 5. All physical examinations after Visit 1 will be abbreviated and limited to the respiratory system only. All physical exam data will be listed.

9.5. Electrocardiogram

Qualitative assessments of electrocardiograms (ECG) conducted at Visit 1, Visit 2, Visit 6, and Visit 7 will be summarized by treatment group and by visit according to the number and percentage of patients reporting an ECG result in each result category. These assessments will be reported as normal, abnormal-not clinically significant, or abnormal-clinically significant.

10. Pharmacokinetics

All presentations of data related to pharmacokinetics will be presented for the PK Concentration Population.

Individual plasma concentrations of S-600918 and its metabolite S-600918 acyl glucuronide will be listed with the actual time elapsed from administration of the last dose by patient and plotted against the actual time elapsed from the last dose. In addition, plasma concentrations of S-600918 and S-600918 acyl glucuronide within 20 to 28 hours after the last dose will be summarized as plasma trough concentrations (C_{trough}) by dose and scheduled visit (Visit 4 and Visit 6) with N, Mean, SD, and coefficient of variation (CV%, calculated by SD/Mean × 100); geometric mean (Geometric Mean) and coefficient of variation for geometric mean (CV% Geometric Mean); and median, minimum (Min) and maximum (Max) values. The CV% Geometric Mean will be calculated according to the following formula: CV% Geometric Mean = [exp (sd²) - 1]^{1/2} × 100, where sd is the standard deviation for natural log (In) - transformed data.

The relationships between C_{trough} and dose will be presented graphically by scheduled visit (Visit 4 and Visit 6) for S-600918 and for S-600918 acyl glucuronide. If C_{trough} is below the lower limit of quantitation, Mean, SD, CV%, Min, Median, and Max will be calculated as 0, and that value will not be included in the calculation of Geometric Mean and CV% Geometric Mean.

Plasma drug and metabolite concentrations determined in blood samples obtained outside of allowable time windows will be included in PK analyses and will not be handled as missing data. Individual plasma concentrations, if deemed to be anomalous, may be excluded from the analysis at the discretion of the PK analyst. Any such exclusion will be communicated to the sponsor and clearly represented in the study report along with justification for exclusion.

Descriptive statistics for Ctrough will be presented as follows:

- N: no decimal place
- Mean, Geometric Mean, SD, median, Min, and Max: same precision as per the observed values.
- CV% and CV% Geometric Mean: one decimal place

11. Pharmacodynamics

There are no pharmacodynamic analyses planned for this study.

12. Interim Analysis

No Interim analysis is planned for this study.

13. Changes in the Planned Analysis

There are no changes in the planned analyses described in the protocol within this SAP.

14. Appendices

